Who will recruit subjects for this study?

Ρ

PI's staff

Describe how research population will be identified, recruitment procedures, any waiting period between informing the prospective participant and obtaining consent, steps taken to minimize the possibility of coercion or undue influence and consent procedures in detail.

Legal and Ethics Requirements: This study is being conducted under a FDA Investigational New Drug Application using an IND originally obtained by [name] and since transferred to [name] (IND # 102,843). All study procedures will be performed under this IND number.

The Investigators will be responsible for obtaining an Informed Consent signed by each patient or his/her legally authorized representative prior to his/her participation in the study in accordance with the Code of Federal Regulations, Title 21, Part 50.20. Informed Consent will be obtained from a patient or his/her legally authorized representative after a full explanation of the purpose of the study, the risks and discomforts involved, potential benefits, etc. have been provided by the Investigator or designee, both verbally and in writing. The person who signed the consent will be given a copy of the signed consent form. The lack of long-term follow-up information regarding the effects of Omegaven will be discussed.

Non-English speaking families will be provided with a consent form in their language. Spanish speaking families will have a full-length Spanish consent form. Speakers of other languages will have an approved short consent form downloaded from the IRB website that is used in combination with a translator. In this circumstance, the parent will sign the foreign language Short Consent Form. The PI or Co-Inv Designee will sign the full length English consent form. The translator will sign both the foreign language short consent form and the English consent form. If the translation service was provided by telephone or video-conferencing, the consent forms (both English and foreign language versions) will be faxed to the translator for signature and faxed back to us. Copies of both consent forms will be provided to the parent to keep.

For any exception patients that are included with specific IRB permission, the use of Omegaven will be explained to the family as with all subjects; however, special mention will be made of the patient's exception status and why we are using Omegaven anyway even though he/she doesn't meet the inclusion criteria.

A waiver of consent is requested for subjects in the historical control subgroup only. Details about this waiver are attached in Section S.

Are foreign language consent forms required for this protocol?

Yes

Which of the following ways will you document informed consent in languages other than English? Short-Form consent documents

J3. Privacy and Intrusiveness

Will the research involve observation or intrusion in situations where the subjects would normally have an expectation of privacy?

No

J4. Children

Will children be enrolled in the research?

Yes

J5. Neonates

Will non-viable neonates or neonates of uncertain viability be involved in research?

No

J6. Consent Capacity - Adults who lack capacity

Will Adult subjects who lack the capacity to give informed consent be enrolled in the research? No

J7. Prisoners

Will Prisoners be enrolled in the research?

No

Section K: Research Related Health Information and Confidentiality

Will research data include identifiable subject information?

Yes

Information from health records such as diagnoses, progress notes, medications, lab or radiology findings, etc.

Yes

Specific information concerning alcohol abuse:

No

Specific information concerning drug abuse:

No

Specific information concerning sickle cell anemia:

No

Specific information concerning HIV:

No

Specific information concerning psychiatry notes:

No

Demographic information (name, D.O.B., age, gender, race, etc.):

Yes

Full Social Security #:

No

Partial Social Security # (Last four digits):

No

Billing or financial records:

No

Photographs, videotapes, and/or audiotapes of you:

No

Other:

No

At what institution will the physical research data be kept?

Texas Children's Hospital - Pavilion for Women

How will such physical research data be secured?

physical data will be kept in locked storage cabinets and closely monitored.

At what institution will the electronic research data be kept?

PHI will be kept on password protected, locked databases that may be accessed on a Baylor College of Medicine secured server.

Such electronic research data will be secured via BCM IT Services- provided secured network storage of electronic research data (Non-Portable devices only):

Yes

Such electronic research data will be secured via Other:

No

Will there be anyone besides the PI, the study staff, the IRB and the sponsor, who will have access to identifiable research data?

No

Please describe the methods of transmission of any research data (including PHI, sensitive, and non-sensitive data) to sponsors and/or collaborators.

Coded information will be shared with the DSMB utilizing secure email. No patient identifiers will be available.

Will you obtain a Certificate of Confidentiality for this study?

No

Please further discuss any potential confidentiality issues related to this study.

Subject identifiers will be destroyed at the earliest opportunity after the FDA has reviewed all data submitted to them and does not request additional data.

Section L: Cost/Payment

Delineate clinical procedures from research procedures. Will subject's insurance (or subject) be responsible for research related costs? If so state for which items subject's insurance (or subject) will be responsible (surgery, device, drugs, etc). If appropriate, discuss the availability of financial counseling.

Texas Children's Hospital will obtain the product from Germany for inpatient use. Families will be billed for the cost of the medication based on an approval for this obtained via the FDA. Families will be informed of the costs. All other costs routinely associated with parenteral nutrition will continue as always to be the responsibility of the patient.

Subjects will be billed for the Omegaven® at home just as they are billed for it while hospitalized at TCH. Thus far, we are not aware of any Medicaid rejections of Omegaven® in our population and anticipate that Medicaid will continue to cover the cost for home use. Families will be informed of the costs. All other costs routinely associated with parenteral nutrition will continue as always to be the responsibility of the patient. Baylor College of Medicine and Texas Children¿s Hospital will not profit from this study.

If subjects will be paid (money, gift certificates, coupons, etc.) to participate in this research project, please note the total dollar amount (or dollar value amount) and distribution plan (one payment, pro-rated payment, paid upon completion, etc) of the payment.

Dollar Amount:

0

Distribution Plan:

Section M: Genetics

How would you classify your genetic study?

Discuss the potential for psychological, social, and/or physical harm subsequent to participation in this research. Please discuss, considering the following areas: risks to privacy, confidentiality, insurability, employability, immigration status, paternity status, educational opportunities, or social stigma.

Will subjects be offered any type of genetic education or counseling, and if so, who will provide the education or counseling and under what conditions will it be provided? If there is the possibility that a family's pedigree will be presented or published, please describe how you will protect family member's confidentiality?

Section N: Sample Collection

SAMPLE: Serum

What is the purpose of the sample collection?

Measurement of triene/tetraene level to assess essential fatty acid deficiency

For blood draws, specify the amount drawn, in teaspoons, at each visit and across the course of the subjects entire participation time.

After every 4 weeks that the subject remains without any enteral nutrition intake at all while hospitalized, 0.5 mL of blood will be taken for triene:tetraene ratios to determine essential fatty acid deficiency. No additional blood draws will be done for outpatients receiving Omegaven.

Potentially, if the subject cannot tolerate any enteral nutrition intake throughout the entire 5 month period of Omegaven, a total of 2.5 mL (less than 1 tsp) of blood may be taken.

Is there the possibility that cell lines will be developed with this sample? No

Sample will be obtained from:

Will the sample be stripped of identifiers?

No

If sample will be released outside the hospital:

Will sample be released to anyone not listed as an investigator on the protocol? Will the information be identifiable, coded or de-identified?

N/A

Will sample material be sold or transferred to any third parties? Will the information be de-identified?

N/A

If sample will be banked for future use:

Where will the sample be banked and for how long?

N/A

Does the banking institution have an approved policy for the distribution of samples?

N/A

If the entire sample will NOT be used during the course of this research study:

Will the remaining tissue be discarded? If not what will be done with the remaining sample after study completion and how long will the sample be kept?

Samples are discarded at the end of the study.

Will samples be made available to the research subject (or his/her medical doctor) for other testing?

No

If a subject withdraws from the study:

Will subject have the option to get the remaining portion of their sample back?

No

Will samples be destroyed? If not, will they be kept anonymously? What will happen to the sample if the subject revokes authorization?

Samples will be discarded.

Will data obtained from their sample be deleted? What will happen to the sample if the subject revokes authorization? Data will not be used in the final analysis.

Will study data or test results be recorded in the subject's medical records?

Will results of specific tests and/or results of the overall study be revealed to the research subject and or his/her doctor?

Please identify all third parties, including the subject's physician, to receive the test results. N/A

Section O: Drug Studies

Does the research involve the use of ANY drug* or biologic? (*A drug is defined as any substance that is used to elicit a pharmacologic or physiologic response whether it is for treatment or diagnostic purposes)

Yes

Does the research involve the use of ANY gene transfer agent for human gene transfer research?

No

O1. Current Drugs

Drug: Omegaven

Is this study placebo-controlled?

No

Will the research involve a radioactive drug?

No

Section P: Device Studies

Does this research study involve the use of ANY device? No

Section Q. Consent Form(s)

None

Section R: Advertisements

None

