To compare with our chart review data: In the historical controls, infection risk was 37/2700 = 0.0137. Therefore, current frequency of infection (0.0065 as shown above) is 48% of the historical rate. Rate of infection of the current Omegaven group total is 2/11 babies with a positive blood infection vs. 42/66 in chart review (P less than 0.05). Of note is that the data from Boston similarly shows a reduction to about 50% of the baseline infection rate after using Omegaven. In addition, based on historical control data and data from the subjects in H-21344, patients with a conjugated bilirubin >6 mg/dL were highly likely to go on to have a conjugated bilirubin >10 mg/dL. Of those with a conjugated bilirubin greater than 10 mg/dL, deaths from liver related causes from the chart review were 6/19 versus 0/5 so far among those completing the Omegaven course. Overall mortality was 11/66 in chart review versus 1/12 so far on Omegaven. These values are extremely similar to the results from Boston. Mean time of resolution among survivors in our chart review was 48 ± 50 (n=42) vs. 31 ± 180 so far on Omegaven.

In protocol H-21344, we have been monitoring all liver function tests and triglyceride levels. All of these show marked rapid improvement on Omegaven. The tetraene/triene ratio was obtained and as noted above was normal on our 5 infants to date who were not receiving 1-2% of calories from EFA. As noted, the Boston group found no long-term abnormalities in any patients in this level out of over 50 studied to date.

Neurodevelopmental outcome testing is offered at our NICU to all at-risk infants which would include most if not all of these babies. However, as this is a compassionate use, not a controlled trial, and given the population is risk factors, it is estimated that nearly 100% of infants will have some developmental delay. There is no method by which this trial can isolate the therapy as contributing to the improvement or worsening of any developmental outcomes. However, given the severe effects of long-term growth failure on developmental outcomes, it is our best judgment that outcomes will be improved.

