Children

Vulnerable populations require special protections. How will you obtain informed consent, protect subject confidentiality, and prevent undue coercion?

Each family will have the severity of their child's condition explained to them and the available data regarding the benefit of the novel preparation explained using the preliminary safety and efficacy data from Boston Children's Hospital and TCH. Families will have the potential risks and benefits of the product explained. The lack of long-term follow-up information regarding the effects of Omegaven will be discussed.

Non-English speaking families will be provided with a consent form in their language. Spanish speaking families will have a full-length Spanish consent form. Speakers of other languages will have an approved short consent form downloaded from the IRB website that is used in combination with a translator. In this circumstance, the parent will sign the foreign language Short Consent Form. The PI or Co-Inv Designee will sign the full length English consent form. The translator will sign both the foreign language short consent form and the English consent form. If the translation service was provided by telephone or video-conferencing, the consent forms (both English and foreign language versions) will be faxed to the translator for signature and faxed back to us. Copies of both consent forms will be provided to the parent to keep.

E3. Pregnant woman/fetus

Will pregnant women and/or fetuses (as described in 45 CFR 46 Subpart B) be enrolled in the research? No

E4. Neonates

Will neonates of uncertain viability or nonviable neonates (as described in 45 CFR 46 Subpart B) be enrolled in the research?

E5. Children

Will children be enrolled in the research?

Yes

Section F: Design/Procedure

F1. Design

Select one category that most adequately describes your research:

z.z) ARCHIVED DO NOT USE - Other: Compassionate Use

Discuss the research design including but not limited to such issues as: probability of group assignment, potential for subject to be randomized to placebo group, use of control subjects, etc.

Infants and children who meet the inclusion criteria specified below will be offered the possibility of enrollment.

Inclusion Criteria:

- 1. Be greater than 10 days old and less than 18 years of age
- 2. Conjugated bilirubin greater than 2 mg/dL
- 3. Be expected to require intravenous nutrition for at least an additional 28 days

Exclusion Criteria:

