
Dose Modification Hypertriglyceridemia: If hypertriglyceridemia develops, defined as serum triglyceride levels > 300 mg/dL, the following will be considered prior to reducing the dose: a) If the level was obtained while the patient was receiving a continuous 24- hour infusion of Omegaven, the total dose should be infused over 20 hours, and a repeat serum triglyceride level obtained prior to resuming the infusion 4 hours later. b) Other sources of hypertriglyceridemia should be considered and addressed (drugs, renal disease) If necessary if the triglycerides continue to remain high despite the aforementioned interventions, a dosage reduction of 25% will be considered.

Duration of Therapy Patients will remain on Omegaven until weaned from PN. In the event that a patient who has been

listed for a liver or liver/intestinal transplant has an organ become available, the participation in this protocol will not preclude them from receiving the transplant. Omegaven will not be administered post transplant.

If the infant no longer is requiring any TPN, then the Omegaven will be stopped regardless of bilirubin. If the bilirubin is less than 2 mg/dL but the child still requires TPN, then the Omegaven will be continued up until the infant no longer requires TPN. The reason for stopping Omegaven when the infant no longer requires TPN is that this would be the only reason many infants would still need IV access and therefore the risk of maintaining IV access only for the medication is likely to exceed the benefit of Omegaven at that point.

Resumption of Omegaven: See Attachment Titled "Amendment 2016.doc" for full details.

Home Use of Omegaven: In order for a subject to receive the Omegaven® at home through the home health care agency, subjects will first be required to be admitted to TCH for 48 hours in initiate the administration of the Omegaven®. This will allow time for observation of any unexpected side effects and for parents to be provided education on home TPN and Omegaven.

If a subject has already received Omegaven® either at TCH or at another hospital, they will not be required to be admitted for the 48 hour inpatient admission prior to starting Omegaven® at home. Parent training will occur during the previous hospital admission and will continue through the TCH Pediatric Intestinal Rehabilitation Clinic.

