Lab monitoring will typically be done every week to two weeks at home and at each clinic visit. Typical lab monitoring will include BUN, CO2, creatinine, glucose, serum chloride, serum potassium, serum sodium (Chem 7), serum calcium, serum phosphorus, serum magnesium, triglycerides, CBC: WBC or leukocyte count, WBC differential count, RBC or erythrocyte count, Hct, Hbg, MCV, MCH, MCHC, red cell distribution width (RDW), platelet count, and mean platelet volume (MPV), and a liver panel: ALT, AST, GGT, AP, albumin, total protein, direct bilirubin (conjugated), total bilirubin, lactic acid dehydrogenase (LDH), and prothrombin time (PT).

Routine evaluations done through the home health service will be continued as usual. If the home health team or TCH Pediatric Intestinal Rehabilitation Clinic Team discovers any unexpected problem(s) involving a risk to the subject or others that are potentially liver-related or Omegaven®-related, the study physician and study coordinator will be immediately notified so that a report can be sent to the IRB and the FDA within 24 hours.

If a subject is consented under the ¿home use¿ consent form and is subsequently readmitted to TCH, the Omegaven and monitoring will continue as discussed for the inpatient use and a specific inpatient use consent form is not necessary. All subjects who are receiving Omegaven on home-use protocol, if re-admitted to the hospital will be re-consented for inpatient use of Omegaven, irrespective of the duration of discharge from the hospital.

Exception Status: If a subject does not meet inclusion criteria, data will still be collected however it will not be included as part of our overall data in terms of time to resolution. Data will still be reported to the FDA in our annual report to them and noted as a exception.

Data from 66 non-Omegaven patients (January 1, 2006 and April 1, 2007) will be recorded to serve as historical controls. Data will be coded to decrease the risk of loss of confidentiality. Codes to identify patients will be kept separate from the rest of the data files, all of which will be maintained in password protected servers and locked file cabinets. Data will include: date of birth, date of admit, birth weight, birth length, birth head circumference, gestational age, admit weight,

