admit length, admit head circumference, gender, race/ethnicity, singleton or multiple birth status, medical and surgical history, type and volume of feeds, age at critical time points of feeds including first feeds, full feeds (defined as 150 ml/kg), maximum volume feeds if

Section G: Sample Size/Data Analysis

G1. Sample Size

How many subjects (or specimens, or charts) will be used in this study?

Local: 376 Worldwide: 376

Please indicate why you chose the sample size proposed:

We propose to enroll all eligible subjects that meet study criteria over the next year. We expect this to be 30 subjects per year based on recent admissions. We have requested the sample size to be increased to 376 subjects. This is based on our previous enrollments. In the past we have enrolled 25-35 subjects every year, hence we have increased the sample size from 346 to 376.

While awaiting the commercial availability of Omegaven following its approval by the FDA we will continue enrollment (both inpatient and home use including an increase in referrals). Hence, we have decided to extend the enrollment to 376 subjects, including the 66 additional subjects requested by the FDA for historical control purposes.

G2. Data Analysis

Provide a description of your plan for data analysis. State the types of comparisons you plan (e.g. comparison of means, comparison of proportions, regressions, analysis of variance). Which is the PRIMARY comparison/analysis? How will the analyses proposed relate to the primary purposes of your study?

We will be calculating for outcome analysis:

- 1. Total days of TPN
- 2. Maximum conjugated bilirubin
- 3. Time to resolution of bilirubin or death/transplant
- 4. Positive blood cultures

Section H: Potential Risks/Discomforts

H1. Potential Risks/Discomforts

Describe and assess any potential risks/discomforts; (physical, psychological, social, legal, or other) and assess the likelihood and seriousness of such risks:

Potential Risk of Omegaven Treatment

No complications from Omegaven have occurred in any of the approximately 1,000 infants who have received it to date.

Omegaven has been studied in animal pre-clinical models as well as Phase I, II, III, and post marketing human trials in both Europe and Asia. Prolonged bleeding time and an inhibited platelet aggregation can occur. It should not be administered to patients known to be allergic to fish or egg protein.

Contraindications to Omegaven include the following:

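### Total TPN days (G2, outcome 1) has no time origin and no rule for death or transplant, so a literal count is cut short by death and can move against the group that survives better

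*Combined protocol and SAP*

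**What the plan says.** The Section G2 form asks for the types of comparison and "Which is the PRIMARY comparison/analysis". The answer is a list of four outcomes. The first is "Total days of TPN". The third is "Time to resolution of bilirubin or death/transplant". No outcome is named primary, and no test, comparison or direction of benefit is given.

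Other sections bear on the first outcome:

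- **Comparator (Section F2).** "Data from 66 non-Omegaven patients (January 1, 2006 and April 1, 2007) will be recorded to serve as historical controls". Section G1 adds that the FDA asked for them.
- **Mortality (Section C).** "Overall mortality was 11/66 in chart review versus 1/12 so far on Omegaven".
- **Entry (Section F1).** Treated subjects must have "Conjugated bilirubin greater than 2 mg/dL" and must "Be expected to require intravenous nutrition for at least an additional 28 days". The purpose in Section D is treatment of PN-associated cholestasis, so PN will ordinarily have begun before the first dose.
- **End of treatment (Section F2, Duration of Therapy).** "Patients will remain on Omegaven until weaned from PN". Omegaven is not given after transplant. The section does not say whether PN continues then.

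**The concern.** A count of days on PN stops when the infant is weaned, and also when the infant dies on PN. A plain total does not tell these apart: an infant who dies on day 20 contributes fewer days than one weaned alive on day 90. Preventing a death on PN can only lengthen that infant's count. The survival benefit the protocol hopes for would therefore push this outcome upwards, and a reader who takes fewer days as better would read that as harm or as lack of effect.

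The missing start date adds a second problem. On its natural reading, a total includes PN days before the first dose, which the drug cannot change.

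If the rule is settled only after the data are seen, the answer can depend on which rule is picked. Restricting to survivors is not a safe default. Section C already summarises time to resolution among survivors in the chart review, and conditioning on survival is a bias of its own.

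**Working it through.** The plan states no figure for TPN days, so there is none to reproduce. The check asks how far mortality alone could move the mean.

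**Inputs from the documents (Section C)**
- Control mortality: 11/66 = 16.7%.
- Omegaven mortality: 1/12 = 8.3%.
- Difference: 2/12 − 1/12 = 1/12.

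**Assumed inputs (not in the documents)**
- Mean PN days in infants who die, D: 20 to 40.
- Mean PN days in survivors, S: 60 to 120.
- D and S are the same in both groups, so the drug has no effect on weaning, and deaths occur on PN.

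**Formula.** With mortality p, mean TPN days = p × D + (1 − p) × S. Treated minus control is therefore (p_control − p_treated) × (S − D) = (S − D)/12.

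**Results**
- Smallest gap, S − D = 60 − 40 = 20: 20/12 = +1.7 days.
- Largest gap, S − D = 120 − 20 = 100: 100/12 = +8.3 days.
- Worked case, D = 20 and S = 90: control (1/6) × 20 + (5/6) × 90 = 78.3; treated (1/12) × 20 + (11/12) × 90 = 84.2; difference +5.8.

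Each further 12 days of gap between S and D adds one day. If D equals S, the shift is zero. If infants who die had longer courses than survivors, the formula turns negative; with S = 60 and D = 90 it gives −30/12 = −2.5.

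**Cross-check with competing hazards.** Assume a constant weaning hazard with mean m days, the same in both groups, and a constant death hazard that yields mortality p. Mean days on PN are then m × (1 − p).
- m = 60: 60 × 5/6 = 50.0 versus 60 × 11/12 = 55.0, difference +5.0.
- m = 90: 90 × 5/6 = 75.0 versus 90 × 11/12 = 82.5, difference +7.5.

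Both lie within the range above.

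**Projected mortality.** Section C also estimates 35 to 75% mortality falling below 10%. Taking 10% for treated infants, the same model gives:
- 35% versus 10%: 0.25 × 60 = +15.0 to 0.25 × 90 = +22.5 days.
- 75% versus 10%: 0.65 × 60 = +39.0 to 0.65 × 90 = +58.5 days.

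That estimate is for infants with conjugated bilirubin above 6 mg/dL who are likely to need two more weeks of TPN. Section F1 now admits infants above 2 mg/dL, so these figures show only what the protocol's own projection would imply in that narrower group.

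**Precision.** For 1/12 versus 11/66, Fisher's exact test gives p = 0.68. The ranges above vary the assumed durations or mortality and carry none of this sampling uncertainty.

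**The case against.** The strongest reply is that G2 states no scoring rule. A reader might infer that the plan scores an early death as a short course and counts pre-treatment days. The documents do not say so; both follow from reading an undefined outcome literally. Section C counts days of therapy separately for the earlier protocol (307 in total), so a count from the first dose is also possible. This reply stands, and it is why the point concerns a missing definition and not a documented rule.

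A reader might also infer that Omegaven will look worse. No section says that fewer TPN days is success. The only stated measure of success, in the DSMB text of Section H1, is improvement in biochemical markers and avoidance of end-stage liver failure. Outcome 3 would put death and transplant beside the TPN count, and a bias of this kind would not create a false claim of benefit. These points limit the consequence. They do not make the count interpretable.

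Three further inferences go beyond the documents:
- **TPN ends at transplant.** Section F2 says only that Omegaven is not given afterwards.
- **Controls were exempt from the 28-day expectation.** The text shown does not say whether they were. The description of control data breaks off before G1, and the chart review itself is not among the documents. The criterion is also a clinical expectation, not an observed minimum.
- **The size is known.** Nothing in the documents supports the assumed durations, and the mortality gap rests on 12 infants. Section C expects most home-use subjects to receive Omegaven for at least 6 months, which lies outside the assumed survivor range.

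**Conclusion.** The point holds as a gap in definition with a predictable direction. Outcome 1 lacks a time origin and a rule for death or transplant, while outcome 3 shows that the authors had both events in view. A literal count is cut short by death and includes PN days before the first dose.

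The direction against Omegaven depends on four conditions: fewer days is read as better, treated subjects are compared with the historical controls, deaths occur on PN after shorter courses than those of survivors, and mortality is lower on Omegaven. Under these conditions, with the reported mortality and the assumed durations, the shift is +1.7 to +8.3 days with no effect on weaning. That figure is illustrative: its size is uncertain, and even the sign of the mortality gap is not established by 12 infants.

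The outcome is one of four and not named primary, so this is something the plan should correct. It does not undermine the study as a whole.

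**What to change.** In G2, replace or supplement outcome 1 as follows:

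1. **Index date.** State one rule that can be applied to treated subjects and controls alike.
2. **Outcome.** Time from the index date to weaning from PN alive, reported as cumulative incidence with death and transplant as competing events. Days alive, transplant-free and PN-free within a fixed window is an alternative.
3. **Late entry.** Count treated subjects as at risk only from their first dose, so that PN days before treatment are not credited to it. Cumulative incidence handles this more directly than the fixed-window summary.
4. **Limitation.** State that treated subjects were selected for an expected 28 or more further PN days, and either document whether controls were or say that this is not known. Do not use a landmark that drops early deaths, since those are the deaths at issue. A prospective expectation of this kind cannot readily be reconstructed from 2006-2007 charts.

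The cost is a change of analysis wording and a standard competing-risk method, with no change to treatment. Outcomes 1 and 3 already call for PN duration, death and transplant. The downsides are a slightly less simple summary than a mean number of days, and the need to confirm that PN stop dates are available for the controls.
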